**Donors:**

Blood samples from donor subjects will also be obtained at either the time of randomization or post-surgery during standard-of-care follow-up appointments. These donor leukocytes will be used as stimulator cells in studies of functional activity of recipient T-cells. These samples will be processed in the principal investigator's research laboratory.

---

### **Safety:**

Safety Endpoints: The primary safety endpoints will be assessed on the AEs and SAEs that are observed throughout the trial.

For the purpose of this clinical trial, the National Cancer Institute Common Terminology Criteria for Adverse Events v3.0 (CTCAE), dated December 12, 2003, will be used to grade all adverse events.

### **Recording of Adverse Events**

At each contact with the subject, the investigator/member of investigator's team will seek information on adverse events by specific questioning and, as appropriate, by examination. Information on all adverse events will be recorded in the source document, and also in the appropriate adverse event module of the case report form (CRF). All clearly related signs, symptoms, and abnormal diagnostic procedures results should be recorded in the source document, though should be grouped under one diagnosis.

All adverse events occurring during the study period will be recorded. The clinical course of each event should be followed until resolution, stabilization, or until it has been determined that the study treatment or participation is not the cause. Serious adverse events that are still ongoing at the end of the study period must be followed up to determine the final outcome. Any serious adverse event that occurs after the study period and is considered to be possibly related to the study treatment or study participation will be recorded and reported immediately.

### **Stopping Rules**

Subjects developing post-transplant infections (i.e., UTI, CMV, HSV, EBV, HCV, HBV, HIV, PCP), that in the opinion of the investigator are detrimental to the subject and his/her participation in this research trial, will be stopped from participating in this study..

Patient Authorization: This study is to be conducted according to US and international standards of Good Clinical Practice (FDA Title 21 part 312 and International Conference on Harmonization guidelines), applicable government regulations and Institutional research policies and procedures.

This protocol and any amendments will be submitted to a properly constituted independent Institutional Review Board (IRB), (Northwestern University Institutional Review Board), in agreement with local legal prescriptions, for formal approval of the study conduct. The decision of the IRB concerning the conduct of the study will be made in writing to the investigator and a copy of this decision will be provided to the investigator/sponsor before commencement of this study. The investigator will place a list of IRB members and their affiliate in the regulatory binder for the clinical trial.

All subjects for this study will be provided with a printed consent form describing this study and providing sufficient information for subjects to make an informed decision

---

about their participation in this study. This consent form will be submitted with the protocol for review and approval by the IRB for the study. The formal consent of a subject, using the IRB-approved consent form, will be obtained before the subject is submitted to any study procedures. This consent form will be signed by the subject and the investigator-designated research professional obtaining the consent. The subject will be given a signed copy of the informed consent for their records.

**Statistical analysis:**

The primary endpoints of the study are graft function and subpopulations of T cells, including regulatory T cells and B cell subpopulations at 3, 6, 12, 24 and 36 months post kidney transplant. The secondary endpoints of the study include 1) incidence of acute rejection, graft loss, and death at 12, 24 and 36 months post kidney transplant; 2) allograft immunohistopathology and gene expression profiles at 12 and 24 months post kidney transplant.

We will run univariate and bivariate analyses for all variables prior to our main analyses. We will evaluate continuous variables using t-tests or F-tests and categorical variables using  $\chi^2$ . We will examine data distributions and test all variables for linear relationships or non-linear relationships.

Descriptive statistics (means, standard deviation, frequency) and correlations (both Pearson and Spearman) among variables will be calculated for preliminary data assessment.

Necessary transformation and imputations will be carried out based on the raw data distribution.

As missing data are inevitable in a longitudinal study, we will determine whether missing data are MCAR (data are missing completely at random), MAR (data are missing at random), or NMAR (not missing at random). If missing data are MCAR or MAR, it is likely that the standard multivariate computations using PROC MI (multiple imputations) will not result in biased standard error estimates. However, if missing data are NMAR, we will use the "pattern mixture" approach to compute a weighted average of the parameters that are associated with the missing data to estimate what the data would have been.

For the primary objective, we hypothesize that subjects receiving low dose CNI with mTOR inhibitor (Everolimus) will exhibit significantly greater graft function and higher numbers of regulatory T cells as compared to the standard dose CNI+MMF group.

We will utilize both repeated-measures ANOVA and random mixed effect models to compare the trajectory change in graft function and proportion of regulatory T cells over 12, 24 and 36 months between the two experimental groups. The method of estimation will be maximum likelihood (ML).

---

A variety of covariance structures (first order regressive, compound symmetry, Toeplitz, variance components, unstructured) will be carefully examined and compared using the best fitting statistics, such as Akaike's Information (AIC) and Bayesian Information Criteria (BIC). These statistics are likelihood functions and can be compared across models. If, in spite of randomization, distributions of subjects' baseline characteristics are found to be different between the two experimental groups, these variables will be entered as covariates in the statistical analysis.

For the secondary endpoints, we will use logistic regression, Kaplan-Meier method, and Cox proportional hazards models to analyze time-to-event outcomes (acute rejection, graft failure, and death). For allograft immunohistopathology and gene expression profile outcomes, we will first develop a comprehensive immune profile of each participant by longitudinal analysis of frequency and function of T and B cell subsets. We will examine how these correlate with immunohistopathology and alloantibody production using Pearson or Spearman correlations. We will compare correlation coefficients between the two experimental groups using Z -tests to determine the distinct effects of each treatment arm. We will also compare the trajectory changes in cell populations and antibody production over 12, 24 and 36 months using both repeated measures ANOVA and random mixed effect models. All tests will be two-sided, and an error rate of  $\alpha < 0.05$  will be considered statistically significant. All data analyses will be performed using SAS 9.2 statistical software (SAS Inc., Cary, NC).

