The present proposal is designed to investigate the mechanisms of the synergistic effect(s) of low dose CNI and mTOR inhibitors (Everolimus) in controlling alloreactive T and B cells while expanding Tregs.

Our hypothesis, based on published data and our laboratory results (see preliminary data-Supportive documents), is that mTOR inhibitors allow expansion of Tregs and that low exposure to CNI is sufficient to control alloreactive T cells. Decreased exposure to CNI and concomitant increase of Tregs will then translate to improved renal allograft function and histology.

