### **Objectives**

The overall aim of the present study is to prospectively investigate the impact of two maintenance immunosuppressive regimens (both prednisone-free) on subpopulations of T and B cells and on renal allograft function at 12, 24 and 36 months post-randomization. One regimen combines low CNI exposure (tacrolimus) with concentration controlled Everolimus, and the second combines standard dose CNI (Tacrolimus) with MMF.

The primary endpoints of the study are to: 1) evaluate the impact of the two maintenance immunosuppressive regimens on T cells subpopulations, including regulatory T cells and B cell subpopulations, at different time points post renal transplant, and 2) determine the impact of the two regimens on renal allograft function at 12, 24 and 36 months post-randomization (post-transplant). Secondary endpoints of the study are to: 1) evaluate the impact of the two regimens on allograft immunohistopathology gene expression profiles and graft infiltrating cells (memory T cell (CD4+ or CD8+ CD45RO+), TREG (CD4+FoxP3+), memory B cell (CD19+CD27+)) at 12 and 24 months in renal allograft biopsies, and 2) evaluate the impact of the regimens on acute rejection, graft loss and death at 12, 24 and 36 months post-transplant.

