**Twenty (20) subjects will begin low dose tacrolimus with concentration controlled everolimus (treatment arm)**

Tacrolimus will be initiated according to our practice. In this treatment arm, the Tacrolimus dose will be adjusted from day 3 on, to a target whole blood trough concentration of 4 ng/mL to 7 ng/mL. From month 2 until Month 6, the target Tacrolimus trough level will be 3 ng/mL to 6 ng/mL. After month 6, the Tacrolimus dose should be adjusted in order to achieve a target trough level of 2 ng/mL to 5 ng/mL.

From day 5 on, the starting dose of Everolimus (0.75 mg bid) will be increased if the trough level is < 3 ng/mL, or reduced if the trough level is > 8 ng/mL.

All drugs will be administered in an open label fashion.

The following transplant recipient data will be collected at the time of randomization:.  
Demographics: Age at transplantation, sex and race.

Causes of end-stage renal disease

Transplant related information: donor age, histocompatibility and cross match data, viral serology, history of acute rejection and delayed graft function, use of ACEI and/or ARB, level of renal allograft function - estimated GFR ( e-GFR(12) using MDRD formula, proteinuria.

Blood samples will be obtained prior to randomization from all renal transplant recipients for baseline T and B cell functional activity and characterization of the cell subpopulations by flow cytometry.

-All recipients will be routinely followed at our Transplant center with post-transplant labs (SMA7, CBC, and relevant immunosuppression trough levels).

Additional blood will be collected and analyzed for the study at 3, 6, 12, 24 and 36 months post-randomization. If the final blood sample cannot be drawn at the 36 month timepoint, it may be drawn up to 50 months post-transplant. These samples will be used to investigate the impact of the two maintenance immunosuppressive regimens on subpopulation of T cells in comparison with baseline levels. Specifically,

---

we will look at regulatory T cells (Treg: Foxp3+CD4+ CD25bright+) that could have been generated via the two maintenance immunonousuppressive regimens, and correlate the generation of with their function.

RNA from peripheral blood will be also collected and stored for post-hoc analyses of T and B-cell immunoresponse gene expression via gene arrays.

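### The primary family is an open list with no rule for combining outcomes, and the graft-function analysis does not clearly test the stated hypothesis of a higher level

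*Combined protocol and SAP*

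**What the plan says.** **Primary endpoints.** Statistical analysis: "The primary endpoints of the study are graft function and subpopulations of T cells, including regulatory T cells and B cell subpopulations", assessed at 3, 6, 12, 24 and 36 months. Objectives numbers two primary items. The first covers T-cell subsets, "regulatory T cells and B cell subpopulations, at different time points post renal transplant"; the second is renal function at 12, 24 and 36 months. Neither section lists the subsets.

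**Hypothesis.** Statistical analysis expects the everolimus arm to have better graft function and "higher numbers of regulatory T cells as compared to the standard dose CNI+MMF group". Study purpose and rationale gives the mechanism: "mTOR inhibitors allow expansion of Tregs", and the "concomitant increase of Tregs will then translate to improved renal allograft function and histology".

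**Model.** "We will utilize both repeated-measures ANOVA and random mixed effect models" to compare trajectories of graft function and Treg proportion over 12, 24 and 36 months, estimated by maximum likelihood (ML). Covariance is chosen by AIC and BIC, and covariates by observed baseline imbalance. All tests are two-sided at 0.05. Trajectories of cell populations in general appear in the secondary-endpoint paragraph.

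**Measures.** Study design (treatment-arm text) lists "e-GFR(12) using MDRD formula" among the data collected at randomization. For the cells, "Blood samples will be obtained prior to randomization from all renal transplant recipients for baseline T and B cell functional activity", and later samples are to be compared with those baseline levels.

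**Power.** Sample size and power refers to two primary endpoints. With 20 per arm, two-tailed 0.05 and 10% attrition at 12 months, it gives 0.82 for an effect size of 1.0 in graft function and 0.99 for 2.0 in percentage Treg change. It calls the study a pilot.

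**The concern.** Three things are left open that decide whether the trial is called positive.

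1. **What counts.** The endpoint definition admits any T- or B-cell subset at any of five visits; the hypothesis, model and power admit two outcomes. Nothing says whether one or both must succeed.
2. **Which test.** Two models are named and neither governs. No model term or visit is identified as the primary comparison.
3. **Whether the test matches the hypothesis.** The hypothesis concerns how high graft function is. A comparison of trajectories over months 12 to 36 may concern only whether the arms diverge after month 12. An advantage already present at month 12 and then maintained would satisfy the hypothesis and be invisible to that test. Two fair readings could give opposite answers from the same data.

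A lesser point is that Treg is a number in the hypothesis, a proportion in the model and a percentage change in the power statement. A higher proportion does not by itself show more cells.

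**Working it through.** **Inputs.** From the documents: 20 per arm, 10% attrition, two-sided 0.05, effect sizes 1.0 and 2.0, visits at 12, 24 and 36 months. Assumed: equal SD at each visit, compound symmetry, within-subject correlation r = 0.5, 0.7 or 0.9. The readable text gives no correlation.

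**Stated power.** Evaluable n = 20 × 0.9 = 18 per arm, 34 df, noncentrality d × √(18/2) = 3d. A two-sample t-test gives 0.830 at d = 1.0 and above 0.999 at d = 2.0, against the stated 0.82 and 0.99. The figures are therefore close to one unadjusted comparison at one visit.

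**Error rate under each success rule**
- Both must succeed: at or below 0.05.
- Either of two suffices: 1 − 0.95² = 0.0975 if independent; by simulation about 0.09 at correlation 0.5 and 0.07 at 0.9.
- Any of k independent tests: 1 − 0.95^k = 0.143 (k = 3), 0.265 (k = 6), 0.401 (k = 10). The documents give no k, and correlated subsets would give less.

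**Graft function, constant 1.0 SD difference at all three visits, 18 per arm**
- Averaged level: SD of the three-visit mean = √((1 + 2r)/3) = 0.816, 0.894, 0.966, so the standardized difference is 1.225, 1.118, 1.035. Power at 0.05 is 0.946, 0.903, 0.855.
- If 10% loss per year continued (assumed 18, 16, 15 per arm): 0.936, 0.895, 0.851.
- Arm-by-time over 12, 24 and 36 months: the differences do not vary, so the noncentrality is zero and rejection is 0.05 by construction (simulation 0.048, 0.048, 0.047).

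**Treg, baseline included.** The arm differences are now 0, 1, 1, 1, with mean 0.75 and sum of squared deviations 0.75. Noncentrality = (18/2) × 0.75/(1 − r) = 13.5, 22.5, 67.5. With a 3-df F test (102 denominator df), power is 0.87, 0.98 and above 0.99.

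**Slow build (assumed 0.33, 0.67, 1.0 SD).** The mean difference is 0.667 SD. Averaged-contrast power is 0.663, 0.584, 0.521; arm-by-time has about 0.40, 0.61, 0.98.

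**ML in 36 patients.** With complete data and compound symmetry, the ML variance of the averaged contrast is low by a factor of 34/36. A nominal 5% test then has error of about 5.6% with a t reference (34 df) and 6.5% with a normal reference.

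**The case against.** **The two-endpoint count.** A reader might infer that the sections flatly contradict each other. They need not: Objectives numbers two items, so the power section may mean two domains, and the wider cell trajectories already sit in the secondary-endpoint paragraph. What stands is that the cell domain is open-ended and only Treg is hypothesised and powered.

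**The error rate.** A reader might infer that the trial runs at 9.75%. No passage states an either-outcome rule. The hypothesis joins the outcomes with *and*, which fairly reads as both, and a pilot carries less confirmatory weight. The documents apply the pilot label to excuse power for secondary outcomes only, and still set a directional hypothesis and a significance threshold. What stands is that the rule is unstated.

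**The contrast.** A reader might infer that the planned analysis cannot detect a sustained benefit. That holds only if the trajectory comparison excludes baseline and ignores the arm main effect, which both models can estimate. For Treg, the stated comparison with baseline points away from that reading. The documents list an eGFR at randomization but do not say that graft function is analysed as change from it, so the gap bears mainly on graft function.

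**The replacement.** The rationale describes calcineurin-inhibitor injury as progressive, which could favour a widening difference. In the slow-build case arm-by-time beats the average at r = 0.7 and 0.9, and a month-36 level contrast, with a difference of 1.0 SD, would have 0.830. This is a fair limit on the choice of average. It does not weaken the need to name one contrast in advance.

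**Conclusion.** The concern holds in limited form. The primary family is not closed, no success rule is given, and the graft-function hypothesis of a higher level is paired with a comparison that need not test it. Depending on the reading, the error rate for two outcomes lies between at most 5% and 9.75%. The chance of detecting a constant 1.0 SD graft-function benefit lies between about 5% and 0.855 to 0.946. The power range rests on 18 per arm, equal visit SDs, compound symmetry and assumed correlations of 0.5 to 0.9. For Treg the contrast problem is small.

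A reader might also infer that the stated 0.82 is an error. It is not: it agrees closely with 0.830 for a single two-sample comparison. The readable text does not show that it describes the repeated-measures analysis, and the figure not shown may bear on this.

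**What to change.** **Change**
1. In Objectives and Statistical analysis, limit the primary family to graft function (MDRD eGFR) and Treg proportion. Label other subsets and visits secondary or exploratory.
2. State that both outcomes must succeed, each at 0.05. If either suffices, use Holm at overall 0.05: the smaller p-value against 0.025 and, if that succeeds, the other against 0.05.
3. Test graft function with one prespecified between-arm level contrast from the mixed model, for example the average over 12, 24 and 36 months. For Treg, adjust the level contrast for the pre-randomization value. Report arm-by-time and repeated-measures ANOVA as supportive.
4. Replace ML with REML and a small-sample degrees-of-freedom correction, and prespecify the covariance structure and covariates.
5. Reword the Treg hypothesis from number to proportion.
6. Settle these choices before any review of outcome data by arm. Treatment is open label, and Population shows randomization under way by January 2014.

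**Cost.** A text amendment, with no added visits or samples.
- *Both required:* joint power is about 0.83 in single-visit terms at the plan's effect sizes, assuming independent outcomes.
- *Holm:* graft-function power = P(0.025) + [P(0.05) − P(0.025)] × Treg power at 0.025, assuming independence. In single-visit terms P(0.025) = 0.741 and P(0.05) = 0.830. At a Treg effect of 2.0 the result is 0.830, so nothing is lost. With no Treg effect it is 0.741 + 0.089 × 0.025 = 0.743, below the plan's 80% target. For the averaged contrast with no Treg effect it is 0.903/0.840/0.775.
- *Averaged contrast:* it loses power if benefit builds slowly, as shown in the working, so arm-by-time must still be reported.

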### **Study purpose and rationale**

Immunosuppressive therapy with the calcineurin inhibitors (CNI) cyclosporine (CsA) and tacrolimus (Tac), has radically changed the field of organ transplantation. Ironically, although extensively and effectively used for kidney and other solid organ transplants, CsA and Tac cause significant adverse renal side effects: acute and chronic renal dysfunction, hemolytic-uremic syndrome, hypertension, electrolyte disturbances and tubular acidosis. Chronic nephrotoxicity from CNI has been implicated as a principal cause of post-transplant renal dysfunction. It is characterized by an irreversible and progressive tubular atrophy, interstitial fibrosis, and focal hyalinosis of small renal arteries and arterioles. Furthermore, by blocking IL2 production, this class of medications is also associated with a negative impact on generation of regulatory T cells, or (Tregs). (Tregs are an important subpopulation of helper T cells that has been associated with positive immunomodulation and donor specific hypo-responsiveness).

In renal transplant recipients, complete avoidance of calcineurin inhibitors from the time of renal transplant surgery has been associated with increased incidence of acute cellular rejection. The combination of mTOR inhibitors with full dose CNI has been shown to be synergistically nephrotoxic, and has been associated with poor graft outcome. We and other investigators have tested conversion from CNI to mTOR inhibitors with promising results. We have shown that in a prednisone-free immunosuppression regimen, conversion from tacrolimus to mTor inhibitors is safe, and not associated with an increased risk of acute rejection. More importantly, we have shown that it is associated with a persistent increase of regulatory T cells (Data presented at ATC 09 and 2010).

Recently, the A2309 study led to FDA-approval of Everolimus. The A2309 was a study designed to combine reduced dose CsA+Everolimus. Interestingly, the reduced exposure to CsA was not associated with an increased rate of ACR; renal allograft function was well maintained when compared to that of the control group. This study

---

study leads us to question the mechanism(s) behind the efficacy of a low dose CNI with an mTOR inhibitor in preventing acute allograft rejection.

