**Study design**

**Renal Transplant Recipients:**

All recipients will receive the same induction immunotherapy at time of transplant. : Campath (30mg IV x1) will be administered at the time of surgery. Methylprednisolone (500 mg IV) will be administered on the day of transplant and on days 1 (250 mg IV), and 2 (125 mg IV) post-transplant. No further steroids will be given post-transplant unless indicated by the following medical conditions: acute renal allograft rejection, renal diseases necessitating the use of steroids, and other systemic diseases such as rheumatoid arthritis (RA), systemic lupus erythematosus (SLE), and asthma.

Maintenance immunosuppression is administered according to the 1:1 randomization at time of enrollment: 20 subjects will begin **standard dose tacrolimus and MMF (control arm)**

Tacrolimus will be initiated according to our practice. The dose will be adjusted from day 3 on to achieve a target whole blood trough concentration of 8 ng/mL to 10 ng/mL. From month 2 until Month 6, the target tacrolimus trough level will be reduced to 6 ng/mL to 8 ng/mL. After month 6, the target level will be reduced to 4 ng/mL to 8 ng/mL.

MMF dose will be initiated as 1 g b.i.d. (2 g/day). Adjustments should be made for adverse events including but not limited to gastrointestinal intolerance and a decrease in WBC. MMF trough or AUC shall not be used to adjust dosing.

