Kidney biopsy samples will be collected with standard-of-care samples at time of transplant (back table), 3 months, 12 months and at 24 months post-transplant. These will help evaluateand compare the impacts of the two maintenance immunonousuppressive regimens on allograft immunohistopathology. Gene expression profiles will also be analyzed. These samples will be processed in the principal investigator's research laboratory.

Both groups of subjects will be followed through 36-months post-randomization. In addition to monitoring renal allograft function, we will evaluate the incidence of acute rejection, subject and graft survival, incidence of hypertension (HTN), malignancies, opportunistic infections and post-transplant diabetes mellitus (DM).

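### The plan collects a back-table biopsy of each graft but never says how it enters the 12- and 24-month histology comparison; it should be a prespecified covariate for chronic structural lesions.

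*Combined protocol and SAP*

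**What the plan says.** **Endpoint.** The Statistical analysis section lists, as a secondary endpoint, "allograft immunohistopathology and gene expression profiles at 12 and 24 months post kidney transplant". The Objectives section gives the same timing, "at 12 and 24 months in renal allograft biopsies", and adds graft-infiltrating memory T, regulatory T and memory B cells.

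**Samples.** The biopsy paragraph of Study design collects cores "at time of transplant (back table), 3 months, 12 months and at 24 months post-transplant". It says that these will help to evaluate and "compare the impacts of the two maintenance immunonousuppressive regimens on allograft immunohistopathology".

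**Analysis.** For histology, the Statistical analysis section describes correlations with each recipient's immune profile and Z-tests comparing the correlation coefficients between arms. Its trajectory models in that paragraph cover cell populations and antibody production, and histology is not listed.

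**Covariates.** The one rule on baseline adjustment is conditional. If, despite randomisation, "distributions of subjects' baseline characteristics are found to be different between the two experimental groups, these variables will be entered as covariates". The baseline data listed in Study design include donor age but not back-table histology.

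**The concern.** The trial's rationale is about injury that develops under calcineurin inhibitor exposure, which the protocol describes as "irreversible and progressive tubular atrophy, interstitial fibrosis, and focal hyalinosis of small renal arteries and arterioles". Lesions of this kind can already be present in the donor kidney. A reading at month 12 or 24 therefore mixes what the graft brought with what it acquired, and only the second part bears on the hypothesis. The back-table core is taken before the graft has met either regimen, so it is a true baseline for structural lesions.

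The peripheral blood endpoint is to be compared with baseline levels under Study design. Histology also has a baseline sample but no such rule. In a trial of about 20 kidneys per arm, that leaves the structural comparison noisier than it need be. If the arms happen to differ in donor-kidney lesions, nothing in the plan fixes in advance how this will be handled.

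**Working it through.** **Inputs from the documents.** 20 recipients per arm, 1:1 (Study design). Two-sided alpha 0.05 and 10% attrition at 12 months (Sample size and power), so 20 × 0.9 = 18 per arm at follow-up.

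**Input assumed.** Correlation r between the back-table score and the 12- or 24-month score. The documents give none. The main range is 0.3 to 0.6, and the simulation in step 5 uses 0.3, 0.5 and 0.7. Scores are treated as roughly continuous, in SD units.

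**1. The plan's own figure.** The stated power of 0.82 at effect size 1.0 is for graft function. A two-sample t-test (noncentral t) gives 0.869 at 20 per arm and 0.830 at 18 per arm, so 0.82 reproduces to within about one point after attrition. At effect size 2.0, power exceeds 0.999, against 0.99 stated. No power is planned for histology. The only use made of this here is to support 18 per arm as the working size.

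**2. Chance imbalance at baseline.** SE of the arm difference = √(2/n).

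| n per arm | SE (SD) | 95% range (1.96 × SE) | P(difference beyond ±0.5 SD) = 2[1 − Φ(0.5/SE)] |
|---|---|---|---|
| 20 | √(2/20) = 0.316 | ±0.62 | 0.114 |
| 18 | √(2/18) = 0.333 | ±0.65 | 0.134 |

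An imbalance of 0.5 SD shifts the unadjusted later difference by 0.5r: 0.15 SD at r = 0.3 and 0.30 SD at r = 0.6. The expected shift over all randomisations is zero.

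**3. Precision available from adjustment.** Residual variance ratio = 1 − r². Estimating the slope at 18 per arm multiplies this by about 33/32.

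| r | 1 − r² | Reduction | With slope: (1 − r²) × 33/32 | Net reduction |
|---|---|---|---|---|
| 0.3 | 0.91 | 9% | 0.938 | about 6% |
| 0.6 | 0.64 | 36% | 0.660 | about 34% |

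The difference detectable with 80% power at 18 per arm (normal approximation) is (1.96 + 0.84) × 0.333 = 0.93 SD unadjusted. Multiplied by √(1 − r²), it becomes 0.89 SD at r = 0.3 and 0.75 SD at r = 0.6, before the slope penalty.

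**4. Change score as an alternative.** Its variance ratio is 2(1 − r): 1.40 at r = 0.3, 1.00 at r = 0.5, 0.80 at r = 0.6. It is worse than no adjustment below r = 0.5, so covariate adjustment is the safer form.

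**5. Is the unadjusted comparison biased?** Simulation with 18 per arm, no regimen effect and 40,000 trials at each of r = 0.3, 0.5 and 0.7 gave a mean difference of about 0 and a type I error of 4.9 to 5.0%. Among simulated trials with a baseline imbalance beyond 0.5 SD, the false-positive rate was about 8%, 13% and 20%. This is offset by lower rates in the better-balanced trials, hence the overall 5%.

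**6. Would the conditional rule catch it?** The rule gives no threshold. If *different* means p < 0.05 on a t-test, the imbalance must reach about 2.02 × 0.316 = 0.64 SD at 20 per arm, or 2.03 × 0.333 = 0.68 SD at 18. An imbalance of 0.5 SD would go unadjusted.

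**The case against.** A reader might infer that lesions inherited from the donor will be counted as regimen effects. The documents do not support that. The protocol states that "Maintenance immunosuppression is administered according to the 1:1 randomization at time of enrollment", so inherited lesions are balanced in expectation, and step 5 shows no bias and a correct error rate. The standard error of a valid unadjusted test already allows for chance imbalance. The three experimental and one control withdrawals before dosing, with replacement (Population), weaken this protection only slightly.

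A reader might also infer that the back-table biopsy has been excluded from the comparison. It has not: Study design names it among the samples that help compare the regimens. The gap is an unspecified method. The conditional covariate rule could take the biopsy in, and donor age is recorded as a rough proxy, so the plan has a partial answer to a visible imbalance. That answer depends on the data, has no threshold and does not secure the precision gain.

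Three further limits stand:

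- The endpoint is wider than structural lesions. A core taken before implantation is not a meaningful reference for recipient cells that infiltrate the graft later.
- The plan writes out correlations and Z-tests for histology, not a model of lesion level by arm. The figures above apply to the between-arm comparison that Study design promises, not to those Z-tests.
- All donors are living (Inclusion Criteria). Inherited lesions may vary little, which would lower r and the gain.

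**Conclusion.** The point holds as a gap in prespecification. A baseline reading of each graft is collected for the regimen comparison, and no analysis says how it is used. The consequence is lost precision and an unplanned response to chance imbalance, not systematic bias.

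The imbalance figures (SE 0.32 to 0.33 SD, 11 to 13% chance of exceeding 0.5 SD) follow from the sample size alone, given a roughly normal arm difference. The precision gain (9 to 36% of residual variance, about 6 to 34% net at 18 per arm) rests on the assumed correlation of 0.3 to 0.6. It concerns chronic structural lesions only.

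This is a modest improvement. The endpoint is secondary, and Sample size and power calls the study a pilot and sets aside power for secondary outcomes. The change is still worth making because the biopsies are already being taken.

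**What to change.** In the Statistical analysis section:

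1. State a between-arm comparison of chronic structural lesions (interstitial fibrosis, tubular atrophy, arteriolar hyalinosis) at months 12 and 24, and name the score used.
2. Prespecify that it adjusts for the same graft's back-table score, by ANCOVA or a mixed model with that score as a baseline covariate, whether or not an imbalance is seen.
3. For recipients whose back-table core is inadequate, use a missing-baseline indicator or mean imputation, so that nobody is dropped. Because the core predates exposure to either regimen, the regimens cannot have caused its inadequacy.
4. If the 3-month biopsy enters the model, treat it as a post-treatment visit and not as a baseline.
5. Do not use the back-table core as the reference for graft-infiltrating recipient cells.

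The cost is plan wording, scoring of cores already collected, and the handling of a few inadequate back-table cores. No new visit or procedure is needed.
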